4.3 Sample Size Justification

While no definitive sample size calculations were performed due to the exploratory nature of the study, a common standard deviation of 3 units and an effect size of 2.25 units on the Aberrant Behavior Checklist should provide 80% power to detect a significant difference at alpha = 0.05 with 30 crossover subjects. If carryover effects or excessive dropouts allow only for a first Period analysis, a sample size of 15 per group during the first period would allow for detection of an effect size of 3.19 units.

4.4 Multiplicity

Since this is an exploratory study of BPN14770, no multiplicity adjustments will be made to any alpha levels used for statistical testing for efficacy endpoints. P-values <0.05 will be used as an indication of treatment effect for all efficacy endpoints.

4.5 Output Production and Validation

All analyses will be performed using SAS V 9.3 or higher (SAS Institute, Inc, Cary, North Carolina, USA). Validation and quality control of the tables and listings, which display the results of the statistical analysis of the data from this study, will follow the appropriate

standard operating procedures (SOPs).

5 SUBJECT DISPOSITION

The number of subjects who are in the safety population, who completed the study, and who discontinued from the study, along with reason of study discontinuation, will be summarized in tabular format by treatment sequence and all subjects for the safety population. Subject disposition information will be displayed for the safety population in a subject listing.

6 DEMOGRAPHIC CHARACTERISTICS

For quantitative variables (e.g., age, height, weight, body mass index [BMI], and Stanford-Binet Full Intelligence scale), summary statistics (number [n], mean, standard deviation [SD], minimum, median, and maximum) will be presented by treatment sequence and all subjects for the safety population. For the qualitative variables (e.g., sex, race, and ethnicity), results will be summarized by treatment group as counts and percentages for the safety population. Individual demographic information for the safety population will be displayed in subject listings.

Version 1.0 16 July 2020

7 MEDICAL HISTORY & PHYSICAL EXAMINATION

Medical history, physical examination findings and neurological examination findings will be displayed for the safety population in a subject listing.

8 COGNITIVE TESTING ANALYSIS

8.1 NIH-Toolbox Cognition Battery (NIH-TCB)

The NIH-TCB is a battery of extensively validated computer-administered cognitive tests with utility across childhood and adolescence, early adulthood, and old age. The NIH-TCB assessments were designed to minimize floor and ceiling effects which often are present in testing batteries designed for the general population. Downward extensions of many of the NIH-TCB tests have been created to allow feasibility down to a mental age of 3. Therefore, there is good reason to believe that the assessments are appropriate for individuals with intellectual disabilities.

NIH-TCB includes the following evaluations/composite scores:

- Picture Vocabulary
- Oral Reading Recognition
- List Sorting Working Memory
- Pattern Comparison Processing Speed
- Picture Sequence Memory
- Flanker Inhibitory Control and Attention
- Dimensional Change Card Set
- Cognition Crystallized Composite Score
- Cognition Fluid Composite Score
- Cognition Total Composite Score

Summary statistics (n, mean, standard deviation, minimum, median, and maximum) will be presented for the observed values and the change-from-baseline values to each posttreatment time point for the uncorrected standard scores, the dext raw scores, and the dext raw percentages if available for each of the above evaluations/composite scores for the ITT population and the completer population. In these displays, baseline will be defined as the last non-missing value obtained prior to first dose of study medication for Period 1, Day 1 predose

The primary uncorrected standard scores are the uncorrected standard scores for cognition crystallized composite, picture vocabulary, oral reading recognition, pattern comparison processing speed, and picture sequence memory. The primary uncorrected standard scores will be analyzed using a mixed effect model. The change from baseline will be used in the model as the dependent variable. The model will include sequence, period, treatment, visit, predose baseline NIH-TCB, baseline Stanford-Binet Full IQ score, and visit by treatment interaction as

Version 1.0 16 July 2020

fixed effects, with subject within sequence as a random effect. This analysis will be done for both the ITT population and the completer population.

In addition, for Period 1 data only, the change-from-baseline to Week 12 will be analyzed using an analysis of covariance (ANCOVA) model with fixed terms for treatment, baseline NIH-TCB and baseline Stanford-Binet Full IQ covariates for the ITT population for the primary uncorrected standard scores.

If a subject could not complete the uncorrected standard flanker control and attention test then the Downward extension was to be used. The same method was to be used for the uncorrected standard dimensional change card sort test. Since the Downward extension scores are not the same as the uncorrected standard scores, they could not be used in the calculations for the cognition fluid composite score or the cognition total composite score. Therefore, the above tests will be denoted as secondary uncorrected standard scores and only summary statistics will be provided.

For the uncorrected standard list sorting working memory score, it was observed that more than 50% of the subjects had missing data at baseline and/or at week 12 after approximately 2/3 of the subjects had completed Period 1. If this trend of sparsity of data remains upon completion of the study, the uncorrected standard list sorting working memory score will also be denoted as a secondary uncorrected standard score and only summary statistics will be provided.

The NIH-TCB results will be displayed in subject listings.

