At the Baseline visit (Period 1, Day 1), prior to randomization, patients will receive an abbreviated physical examination including vital signs. However, these will not be repeated if the Screening and Baseline visits occur on the same day. Cognitive and behavioral evaluations will be performed, and these measurements will be used as a common set of baseline measurements to which post-treatment assessments will be compared for both treatment periods. During both double-blind periods, subjects will receive twice-daily treatment with blinded study medication as randomly assigned at baseline. Doses of study medication should be taken in the morning and at night, at least 6 hours apart and at least 30 minutes prior to or 1 hour after meals. Subjects will return to the clinic at the end of Weeks 2, 6, and 12 for each period. Cognitive and behavioral evaluations will be repeated at Weeks 6 and 12 for each period, with the exception of event-related potentials and eye tracking which will be repeated only at Week 12 for each period. Additionally, subjects will be monitored for adverse events, changes in concurrent medications and suicidality via a telephone call at the end of Week 1 of each period, and one week following completion of Period 2 (concurrent medications and AEs only). During clinic visits, adverse effects will be assessed, and laboratory measures, vital signs, and ECGs will be repeated per protocol. Suicidality risk with also be evaluated during the treatment periods per protocol; if a concern is detected, the subject will be referred for further evaluation and treatment. If a patient discontinues the study before Week 12 of a period, the clinical site will endeavor to collect all assessments to be completed at Week 12.

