4 GENERAL METHODS

4.1 Analysis Populations

Safety Population: All subjects who sign the study-specific informed consent documents and receive at least one dose of study medication.

Intent to Treat (ITT) Population: All randomized subjects who receive at least one dose of treatment and return for at least one follow-up visit.

Version 1.0 16 July 2020

Completer Population (CP): All randomized subjects who complete both treatment periods with no significant protocol deviations.

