4.2 Summarization of Data

Study results will be summarized by treatment group (Placebo or 25 mg BID) or treatment sequence (A-B, B-A), where appropriate.

No imputation of missing data will be performed. No windowing of visits will be performed unless otherwise specified.

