8.6 Aberrant Behavior Checklist (ABC)

ABC is a 58-item parent/caregiver rating scale used to assess behaviors across six dimensions or subscales: irritability, hyperactivity, lethargy/withdrawal, stereotypy, inappropriate speech and social avoidance. Items are evaluated on a four-point Likert scale ranging from 0 (not at all a problem) to 3 (the problem is severe in degree).

Summary statistics (n, mean, standard deviation, minimum, median, and maximum) will be presented for the observed values and the change-from-baseline values to each posttreatment time point for each of the six subscales for the ITT population and the completer population. In these displays, baseline will be defined as the last non-missing value obtained prior to first dose of study medication for Period 1, Day 1 predose.

For each subscale, the change-from-baseline to Week 12 will be analyzed using an analysis of covariance (ANCOVA) model which includes sequence, period, and treatment as fixed factors, subject within sequence as a random factor, and baseline ABC score and baseline Stanford-Binet full IQ covariates for the ITT population and the completer population.

Version 1.0 16 July 2020

In addition, for Period 1 data only, the change-from-baseline to Week 12 will be analyzed using an analysis of covariance (ANCOVA) model with fixed terms for treatment, baseline ABC and baseline Stanford-Binet full IQ covariates for the ITT population for each subscale.

All ABC assessments will be displayed in subject listings.

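### The crossover models in SAP 8.1–8.3 and 8.5–8.9 require a baseline score and an IQ that the two-period treatment contrast does not need, so a subject missing either value would be lost for no gain (CGI-I, 8.4: IQ only)

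*SAP*

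**What the plan says.** For the NIH-TCB scores, SAP 8.1 specifies: "The change from baseline will be used in the model as the dependent variable". The terms are listed thus: "The model will include sequence, period, treatment, visit, predose baseline NIH-TCB, baseline Stanford-Binet Full IQ score, and visit by treatment interaction as". The sentence then closes by classing those terms, and the subject effect, in these words: "fixed effects, with subject within sequence as a random effect". KiTAP (8.2), CGI-S (8.3) and VAS (8.5) follow the same pattern. ABC (8.6), ADAMS (8.7), ERP (8.8) and eye tracking (8.9) are analysed at Week 12 only, without visit terms, but still as change scores. For ABC the model carries "subject within sequence as a random factor, and baseline ABC score and baseline Stanford-Binet full IQ covariates". CGI-I (8.4) is the exception: the observed rating is the outcome and IQ is the only baseline covariate.

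There is one baseline for the whole trial. SAP 2 says of the Day 1 assessments that "these measurements will be used as a common set of baseline measurements to which post-treatment assessments will be compared for both treatment periods".

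On missing data, SAP 4.2 says "No imputation of missing data will be performed". The ITT population in SAP 4.1 is "All randomized subjects who receive at least one dose of treatment and return for at least one follow-up visit", so membership requires neither a baseline score nor an IQ. The SAP has no rule for a missing baseline or IQ and no crossover model without them.

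For List Sorting, SAP 8.1 records that, when about two-thirds of subjects had completed Period 1, "more than 50% of the subjects had missing data at baseline and/or at week 12". If that sparsity persists, the score will receive summary statistics only.

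**The concern.** The SAP does not write the exclusion out, but it follows from the model. Without a baseline there is no change score, and standard mixed-model software drops records with a missing covariate. An ITT subject with usable scores in both periods can therefore be absent from the ITT crossover analysis.

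For such a subject the missing value contributes nothing to the treatment comparison. Baseline score and IQ take the same value in both periods, so they drop out of the within-subject difference on which a crossover rests. The requirement can only lose data from two-period subjects. The sample size in Protocol 11.1 assumes 30 evaluable patients, and Protocol 6.5 does not replace withdrawals, so there is no reserve to absorb losses.

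**Working it through.** **Inputs.** SD 3, effect 2.25 units, 80% power, alpha 0.05 (taken as two-sided), 30 crossover subjects (SAP 4.3; Protocol 11.1, 15 per sequence). The number k of two-period subjects lost for a missing baseline or IQ is not in the documents and is an assumption throughout.

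**1. Endpoints involved.** Modelled endpoints: 5 NIH-TCB + 7 KiTAP + 1 CGI-S + 1 CGI-I + 3 VAS + 6 ABC + 5 ADAMS + 8 ERP + 8 eye tracking = 44. All carry IQ, and 43 (all but CGI-I) are change scores. Of the 43, 5 + 7 + 8 + 8 = 28 are performance-based or physiological and 3 + 6 + 5 + 1 = 15 are rated by a caregiver or clinician.

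**2. Cancellation.** Write the score of subject i in period j as y_ij, the baseline as b_i, and the covariate contribution as βb_i + γIQ_i. Then (y_i1 − b_i) − (y_i2 − b_i) = y_i1 − y_i2, and the covariate contribution is the same in both rows, so it also subtracts out. With a sequence term in the model, two-period subjects inform the treatment effect only through this difference.

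A numerical check used one simulated 30-subject crossover with a random subject intercept, fitted by REML:

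- One visit per period: estimate 2.07864, SE 0.50926. This was identical for change with both covariates, change without, observed score without, and observed score with.
- Two visits with visit by treatment: 2.07864, SE 0.54885. This was identical for change with covariates, change without, and observed score.
- Same two-visit data with 3 baselines and 3 IQs deleted: the planned model used 24 subjects and gave 2.452; the observed-score model used all 30 and still gave 2.079. In this one dataset the SE happened to be lower with 24 (0.528 against 0.549), so the cost has to be judged on expectation, as in step 4.
- Four subjects with Period 1 only (one visit per period): 1.967 (change with covariates), 2.039 (change without) and 1.930 (observed score). Cancellation is exact only for subjects complete in both periods.

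**3. The plan's own figure.** SE = 3 × √(2/30) = 0.775, df = 28, noncentrality 2.25 / 0.775 = 2.90. Two-sided noncentral t power = 80.1%, and the effect detectable with 80% power = 2.248. The stated 2.25 is reproduced. This takes SD 3 per observation with zero within-subject correlation; reading 3 as the SD of the within-subject difference would give 97.7% and would not match the plan.

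**4. Cost of losing k two-period subjects.** SE = 3 × √(2/(30 − k)), df = 28 − k, SE ratio = √(30/(30 − k)).

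| k | n | SE | SE ratio | Power at 2.25 | Effect detectable at 80% |
|---|---|---|---|---|---|
| 0 | 30 | 0.775 | 1.000 | 80.1% | 2.25 |
| 1 | 29 | 0.788 | 1.017 | 78.6% | 2.29 |
| 3 | 27 | 0.816 | 1.054 | about 75% | 2.38 |
| 6 | 24 | 0.866 | 1.118 | 70.0% | 2.54 |

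In 20,000 simulated trials with k = 6, power was 70.5% against 80.3% with all 30. The SE ratio does not depend on the SD assumed; the power figures do.

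**The case against.** The strongest reply is that the loss may never occur. Every efficacy baseline is scheduled before randomization (Protocol 10.3.1). Stanford-Binet is a screening procedure, a result from the previous 6 months may be used, and the scoring is chosen to avoid floor effects (Protocol 8.4). No document shows a missing baseline or IQ on any modelled endpoint. This stands, and it makes the size conditional.

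A reader might infer from the List Sorting remark that about half the baselines are missing. The documents do not support that. The figure combines baseline with Week 12 and gives no baseline share. It concerns a score outside the five primary NIH-TCB scores, and its move to summary statistics is conditional.

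A reader might also calibrate to that figure. With 70% availability, independent at each time point, 1 − 0.7² = 51% would lack baseline and/or one Week 12 value. Then 30 × 0.49 = 14.7 subjects would have both periods and 30 × 0.343 = 10.3 would also have a baseline, an SE increase of √(14.7/10.3) − 1 ≈ 20%. But inability to do a test tends to persist. With missingness driven by a shared ability at latent correlations of 0.5 to 0.9, the increase falls to 10.5% down to 3.9%, and it is zero if missing baselines occur only in subjects who also miss a Week 12 score.

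A further inference is that the lowest-functioning subjects would be lost and the estimate shifted. That is plausible for tests the subject must perform, but it is not documented. It does not reach the 15 caregiver- or clinician-rated change scores, including ABC, on which the power statement rests.

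Finally, the covariates are not idle everywhere. They inform one-period subjects, whom the ITT definition admits, and they serve the Period 1 ANCOVA. That stands and shapes the fix.

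**Conclusion.** The concern holds as a conditional weakness in model specification. Sections 8.1–8.3 and 8.5–8.9 require a baseline score and an IQ, and 8.4 an IQ, for a contrast that needs neither when both periods are observed. The SAP has no rule or alternative model that retains a subject lacking one of them. The cost ranges from nothing, if no such value is missing, to about 5% or 12% in SE and about 5 or 10 percentage points of power if 3 or 6 of 30 two-period subjects are lost. Those counts are illustrations, and the power figures rest on the reading of SD 3 that reproduces the plan's 80%. The practical concern is mainly for NIH-TCB, KiTAP, ERP and eye tracking. The documents do not support saying that contrasts are in fact being discarded, nor putting a 20% SE loss on any modelled endpoint. The change is worth making because it is cheap and loses almost nothing if the problem does not arise.

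**What to change.** In SAP 8.1–8.3 and 8.5–8.9, fit the crossover model to the observed post-treatment score with sequence, period, treatment, visit terms where already planned, and the subject effect, without requiring baseline score or IQ. In 8.4, drop only the IQ requirement. All ITT subjects with post-treatment data then contribute.

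Keep the planned change-score model with covariates as a companion analysis, and report the number of subjects in each. Keep both covariates in the Period 1 ANCOVA (IQ alone for CGI-I), where the comparison is between subjects and they can add precision.

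For List Sorting, judge sparsity for the crossover model on post-treatment scores in both periods, and separately on baseline plus Week 12 for the Period 1 ANCOVA.

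The cost is SAP wording and a few lines of code. Protocol 11.4 ties change from baseline to descriptive statistics and leaves the mixed model open. The statistical downside is a little lost between-subject adjustment for one-period subjects: about 1–1.5% in SE with 3 to 6 such subjects, under assumed correlations, against about 5% saved if three two-period subjects would otherwise be dropped.

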8.2 KiTAP – Test of Attention Performance

KiTAP consists of eight nonverbal subtests measuring different basal as well as higher-order components of attention and executive functioning. Four subtests (i.e., alertness, distractibility, go-nogo, and flexibility) will be utilized in the study. Within each subtest, mean reaction time, standard deviation time, number correct, number error, and number omissions were reported as appropriate.

The primary endpoints are the alertness mean reaction time, distractibility correct (distractor), distractibility errors (distractor), flexibility correct, flexibility errors, go-nogo correct, and go-nogo errors. Summary statistics (n, mean, standard deviation, minimum, median, and maximum) will be presented for the observed values and the change-from-baseline values to each posttreatment time point for the primary endpoints for the ITT population and the completer population. In these displays, baseline will be defined as the last non-missing value obtained prior to first dose of study medication for Period 1, Day 1 predose.

The primary endpoints will be analyzed using a mixed effect model. The change from baseline will be used in the model as the dependent variable. The model will include sequence, period, treatment, visit, predose baseline KiTAP score, baseline Stanford-Binet Full IQ score, and visit by treatment interaction as fixed effects, with subject within sequence as a random effect. This analysis will be done for both the ITT population and the completer population.

In addition, for Period 1 data only, the change-from-baseline to Week 12 will be analyzed using an analysis of covariance (ANCOVA) model with fixed terms for treatment, baseline KiTAP and baseline Stanford-Binet full IQ covariates for the ITT population for the primary endpoints.

All KiTAP assessments will be displayed in subject listings.

8.3 Clinical Global Impression Severity (CGI-S)

CGI-S is a global measure to provide a clinical judgment of a subject's overall condition based on a trained clinician's assessment of cognition, behavior and activities of daily living. The assessment of severity will be made with a 7-point scale: 1, not ill; 2, very mild; 3, mild; 4, moderate; 5, marked; 6, severe; 7, extremely severe.

CGI-S will be summarized by treatment group as counts and percentages at each visit for the ITT population and the completer population. In addition, CGI-S will be summarized by treatment group as counts and percentages at each visit for the Period 1 data only.

Summary statistics (n, mean, standard deviation, minimum, median, and maximum) will be presented for the observed values and the change-from-baseline values to each posttreatment time point for CGI-S for the ITT population and the completer population. In these displays, baseline will be defined as the last non-missing value obtained prior to first dose of study medication for Period 1, Day 1 predose.

CGI-S will be analyzed using a mixed effect model. The change from baseline will be used in the model as the dependent variable. The model will include sequence, period, treatment, visit, predose baseline CGI-S score, baseline Stanford-Binet Full IQ score, and visit by treatment interaction as fixed effects, with subject within sequence as a random effect. This analysis will be done for both the ITT population and the completer population.

In addition, for Period 1 data only, the change-from-baseline to Week 12 will be analyzed using an analysis of covariance (ANCOVA) model with fixed terms for treatment, baseline CGI-S and baseline Stanford-Binet full IQ covariates for the ITT population for CGI-S.

The CGI-S results will be displayed in subject listings.

8.4 Clinical Global Impression Improvement (CGI-I)

CGI-I assessment is a 7-point scale that requires the clinician to assess how much the subject's illness has improved or worsened relative to a baseline state at the beginning of the intervention, and rated as: 1, very much improved; 2, much improved; 3, minimally improved; 4, no change; 5, minimally worse; 6, much worse; or 7, very much worse.

CGI-I will be summarized by treatment group as counts and percentages at each visit for the ITT population and the completer population. In addition, CGI-I will be summarized by treatment group as counts and percentages at each visit for the Period 1 data only.

Summary statistics (n, mean, standard deviation, minimum, median, and maximum) will be presented for the observed values at each posttreatment time point for CGI-I for the ITT population and the completer population.

CGI-I will be analyzed using a mixed effect model and will be used in the model as the dependent variable. The model will include sequence, period, treatment, visit, baseline Stanford-Binet Full IQ score, and visit by treatment interaction as fixed effects, with subject within sequence as a random effect. This analysis will be done for both the ITT population and the completer population.

Version 1.0 16 July 2020

Version 1.0 16 July 2020

In addition, for Period 1 data only, CGI-I will be analyzed using an analysis of covariance (ANCOVA) model with fixed terms for treatment, and baseline Stanford-Binet full IQ covariates for the ITT population at Week 12.

The CGI-I results will be displayed in subject listings.

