Pharmacokinetic and biomarker samples will be collected to at screening and at the end of Period 1 and Period 2. The pharmacokinetic samples are primarily to confirm that study drug is present when expected and to estimate plasma exposure at end of Periods 1 and 2.

Planned Numbers of Subjects

Enrollment of a total of 30 eligible subjects is planned, 15 per treatment sequence.

Study Duration

The total duration of the study for each subject will be up to 29 weeks, including a maximum of 4-week screening period, two 12-week Double-Blind treatment Periods, and a follow-up telephone call approximately 1 week after last treatment.

Protocol: BPN14770-CNS-203 Tetra Discovery Partners, Inc.
Date: 25 June 2018 Confidential

Name of Sponsor/Company:	Tetra Discovery Partners, Inc.
Name of Investigational Product:	BPN14770
Study Title:	A Randomized, Double-blind, Placebo-controlled, 2-period Crossover Study of BPN14770 in Adult Males with Fragile X Syndrome
Study Number:	BPN14770-CNS-203
Study Phase:	Phase 2

Study Procedures:

The Screening Visit will occur up to 28 days prior to the first study drug administration on Day 1. During screening, patients and their parent/legal authorized guardian, if indicated, will review and sign an Informed Consent/Assent form prior to any study procedures being performed. Following confirmation of a prior diagnosis for Fragile X, patients will have information collected regarding their neurological and medical/surgical history, race/ethnicity, social history (tobacco, alcohol, and/or drug use), and use of prescription and over-the-counter medications. Patients will undergo a full physical exam, have vital signs measured, and 12-lead ECG performed. Height, weight, and BMI will also be collected. Fasting blood samples will be collected for chemistry and hematology, as well as biomarkers and pharmacokinetics. Urine will be collected for urinalysis. The Stanford-Binet test will also be administered at screening, as will an assessment of suicidality risk.

At the Baseline visit (Period 1/Day 1), prior to randomization, patients will receive an abbreviated physical examination including vital signs. However, these will not be repeated if the Screening and Baseline visits occur on the same day. Cognitive and behavioral evaluations will be performed and these measurements will be used as a common set of baseline measurements to which post-treatment assessments will be compared for both treatment Periods.

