8.13.2 Timing of Efficacy Assessments

8.13.2.1 Baseline (Period 1/Day 1)

The following exploratory efficacy assessments will be performed at Baseline (Period 1/ Day 1, prior to randomization):

- NIH Toolbox Cognitive Battery for Intellectual Disabilities (NIH-TCB)
- Test of Attentional Performance (KiTAP)
- Clinical Global Impression Severity Investigator rated (CGI-S)
- VAS Rating Scale using patient-specific behavioral anchors
- Aberrant Behavior Checklist (ABC)
- Anxiety, Depression, and Mood Scale (ADAMS)
- Vineland-3 Rating Scale
- Event-Related Potentials (ERP)
- Eye Tracking

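### CGI-I is the only modelled instrument with no baseline severity term; baseline CGI-S could be pre-specified in its Period 1 ANCOVA, a small gain that depends on an unknown correlation

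*SAP*

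**What the plan says.** SAP 8.4 specifies two models for CGI-I.

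- Crossover mixed model: "The model will include sequence, period, treatment, visit, baseline Stanford-Binet Full IQ score, and visit by treatment interaction as fixed effects". The random term is a subject effect nested in sequence.
- Additional Period 1 analysis: an ANCOVA written as a "model with fixed terms for treatment, and baseline Stanford-Binet full IQ covariates for the ITT population at Week 12".

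Neither contains a severity score. CGI-I cannot supply one, because it asks the clinician to judge "how much the subject's illness has improved or worsened relative to a baseline state at the beginning of the intervention" and so has no Day 1 value.

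The companion scale does have a Day 1 value. CGI-S is listed among the assessments made on Period 1 Day 1 before randomization (protocol 8.13.2.1, 10.3.1 and the schedule in 16.1). SAP 8.3 uses it in the CGI-S mixed model: "The model will include sequence, period, treatment, visit, predose baseline CGI-S score, baseline Stanford-Binet Full IQ score". The Period 1 ANCOVA for CGI-S carries it too.

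The remaining modelled instruments follow the same pattern of own baseline plus IQ: NIH-TCB (SAP 8.1), KiTAP (8.2), VAS (8.5), ABC (8.6), ADAMS (8.7), ERP (8.8) and eye tracking (8.9).

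There is one baseline per subject. The protocol synopsis, under Study Procedures, says that "these measurements will be used as a common set of baseline measurements to which post-treatment assessments will be compared for both treatment Periods".

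**The concern.** The Period 1 ANCOVA compares different people, 15 in each sequence. If subjects who start out more severe tend to receive different improvement ratings, leaving severity out keeps that variation in the residual. A chance imbalance in severity between the sequences would then also shift the estimate in the trial actually run.

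The Period 1 analysis may have to carry weight. There is no washout between periods. Protocol 4.2 reports that benefit in the mouse model was still present two weeks after the drug had washed out. Protocol 11.1 and SAP 4.3 both allow for carryover or dropout leaving only the first period usable. SAP 4.4 reads each efficacy endpoint at an unadjusted p<0.05, so a modest change in standard error can change how a result is read. SAP 8.4 gives no reason for leaving out a variable that SAP 8.3 already uses.

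**Working it through.** **1. The plan's own figures.** None is given for CGI-I; the sample-size text concerns ABC. Inputs: SD 3, 80% power, 5% alpha (taken as two-sided), 30 subjects, 15 per sequence (protocol 11.1, SAP 4.3). Noncentral t with 28 df:

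- Crossover: SE = 3 × sqrt(2/30) = 0.775; detectable difference 2.248, against 2.25 stated.
- Period 1 only: SE = 3 × sqrt(2/15) = 1.095; detectable difference 3.179, against 3.19 stated.

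Both reproduce, so the Period 1 design (15 per arm, SD 3, effect 3.19) can serve as a scale for step 2. The SD of 3 is borrowed from ABC and says nothing about CGI-I itself.

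**2. Adding baseline CGI-S to the Period 1 ANCOVA.** Let rho be the partial correlation of baseline CGI-S with Week 12 CGI-I given IQ. The documents give no value, so 0 to 0.5 is shown. The residual variance is multiplied by (1 - rho²). With q covariates and N = 30, the variance of the treatment difference is inflated on average by 1 + q/(N - q - 3):

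- IQ only (q = 1): 1 + 1/26 = 1.0385, 27 df.
- IQ and CGI-S (q = 2): 1 + 2/25 = 1.0800, 26 df.
- SE ratio = sqrt((1 - rho²) × 1.0800/1.0385) = sqrt((1 - rho²) × 1.04).

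Detectable difference and power at 3.19, taking SD 3 as the residual SD given IQ:

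| rho | SE ratio | Change in SE | Detectable difference | Power at 3.19 |
|---|---|---|---|---|
| IQ only | 1 | reference | 3.244 | 78.7% |
| 0 | 1.020 | +2.0% | 3.313 | 77.0% |
| 0.1 | 1.015 | +1.5% | 3.297 | 77.4% |
| 0.2 | 0.999 | -0.1% | 3.246 | 78.6% |
| 0.3 | 0.973 | -2.7% | 3.161 | 80.7% |
| 0.4 | 0.935 | -6.5% | 3.037 | 83.7% |
| 0.5 | 0.883 | -11.7% | 2.870 | 87.6% |

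Break-even on detectable difference is at |rho| = 0.203. A simpler formula that counts only the lost degree of freedom, sqrt((1 - rho²) × 27/26), gives 1.019, 0.972, 0.934 and 0.883 at rho = 0, 0.3, 0.4 and 0.5, so the result does not hang on the choice of inflation factor.

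**3. Adding it to the crossover mixed model.** Day 1 CGI-S is constant within a subject. With both periods observed, the treatment contrast is within-subject and a subject-level covariate cancels from it. A REML simulation of the SAP 8.4 model checked this. It used 30 subjects, two visits per period, unit outcome variance, assumed ICC 0.5, Period 2 missing independently of severity, and 400 runs per scenario:

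| Period 2 missing | rho | Mean SE without CGI-S | Mean SE with CGI-S |
|---|---|---|---|
| 0% | 0.5 | 0.1287 | 0.1287 |
| 10% | 0.5 | 0.1357 | 0.1351 |
| 20% | 0.3 | 0.1422 | 0.1419 |
| 20% | 0.5 | 0.1427 | 0.1415 |

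With complete data the estimates were identical in every run. At 20% missing the reductions are 0.0003/0.1422 = 0.2% and 0.0012/0.1427 = 0.8%.

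**The case against.** The best defence is that nothing here is invalid. CGI-I has its reference to baseline built into the rating, it has no Day 1 score to include, and leaving an optional prognostic covariate out of a supportive analysis at N = 30 is a legitimate choice in an exploratory study. Even the sign of the benefit rests on a correlation that the documents do not give. CGI-S is defined as reflecting cognition among other things (protocol 8.13.1.3.1), so it may overlap with IQ, which is already in the model, and the partial correlation could be small. All of this stands, and it keeps the point minor. It does not remove the asymmetry with SAP 8.3 or the low price of the covariate.

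A reader might also infer more than the documents support:

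- That CGI-I has no baseline adjustment. Both models adjust for baseline IQ; what is missing is severity.
- That CGI-I is the only efficacy instrument treated this way. That holds only among instruments with a specified model. Vineland-3 is listed in SAP 3.2 but has no analysis in SAP 8.
- That precision is being given up for nothing. Below a partial correlation of about 0.2 the added covariate costs precision.
- That chance imbalance biases the Period 1 estimate. Under 1:1 randomization it adds variance; it shifts the estimate only conditionally on the imbalance that occurs.
- That CGI-S and CGI-I come from the same clinician. Protocol 8.13.1.3.2 sets a same-rater rule for CGI-I; no such rule is stated for CGI-S.
- That the main crossover result would improve. Step 3 of the working shows that it would not, to any useful degree.

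**Conclusion.** The point holds as a small improvement to one supportive analysis. The omission of baseline severity from both CGI-I models is certain from the text; the gain from adding it is not. In the Period 1 ANCOVA the standard error would move between about +2% and -12% over partial correlations from 0 to 0.5, with no change near 0.2. The crossover model is essentially unaffected.

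These sizes rest on an assumed partial correlation, on 15 subjects per arm with complete Period 1 Week 12 data, and, for the mixed model, on ICC 0.5 and dropout unrelated to severity. Dropout that depends on severity was not examined.

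**What to change.** In SAP 8.4, add the Period 1 Day 1 CGI-S score as a covariate in the Period 1 Week 12 ANCOVA for CGI-I, using the baseline definition already in SAP 8.3. Adding it to the CGI-I mixed model is optional and would be for consistency only. If the omission is deliberate, one sentence giving the reason is enough. Make the change before unblinding; after that, report the adjusted model as a sensitivity analysis.

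The cost is one model term, one degree of freedom and, on average, at most about 2% in standard error if severity does not predict CGI-I. No new data are needed. Because SAP 4.2 rules out imputation, a subject without a Day 1 CGI-S would drop out of the adjusted analysis, as already happens in SAP 8.3.
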